## 11.4.3 Tumor Lysis Syndrome Prophylaxis

An approved uric acid-lowering agent (e.g. allopurinol) in patients at high risk for tumor lysis syndrome (TLS) due to high tumor burden may be prescribed at the investigator's discretion and according to the IBs.

#### **11.4.4 Contraceptive requirements**

#### Women of childbearing potential

A woman is considered fertile following menarche and until becoming post-menopausal unless permanently sterile. Permanent sterilization methods include hysterectomy, bilateral salpingectomy, and bilateral oophorectomy.

Women in the following categories are not considered of child bearing potential:

- 1. Premenopausal woman with 1 of the following:
  - Documented hysterectomy
  - o Documented bilateral salpingectomy
  - Documented bilateral oophorectomy

Note: Site personnel documentation from the following sources is acceptable:

- o review of patient medical records
- patient medical examination, or
- patient medical history interview.
- 2. Postmenopausal woman:
  - A postmenopausal state is defined as no menses for 12 months without an alternative medical cause. A high follicle stimulating hormone (FSH) level in the postmenopausal range may be used to confirm a postmenopausal state in women not using hormonal contraception or hormonal replacement therapy (HRT). However, in the absence of 12 months of amenorrhea, a single FSH measurement is insufficient.
  - Women on HRT and whose menopausal status is in doubt will be required to use 1 of the non-hormonal highly effective contraception methods if they wish to continue their HRT during the study. Otherwise, they must discontinue HRT to allow confirmation of postmenopausal status before study enrollment.

#### Female patients

Contraception and pregnancy testing are required according the CTFG recommendations:

https://www.hma.eu/fileadmin/dateien/Human\_Medicines/01-

About\_HMA/Working\_Groups/CTFG/2020\_09\_HMA\_CTFG\_Contraception\_guidance\_Version \_1.1\_updated.pdf

WCBP should be advised to avoid becoming pregnant while being treated with Carfilzomib or Ibrutinib. WCBP and / or their male partners should use highly effective contraception methods or abstain from sexual activity during treatment and for 6 months after treatment with Carfilzomib or Ibrutinib. Female patients of childbearing potential must agree to use 1 highly effective method of contraception (as described below). It cannot be excluded that the efficacy of oral contraceptives may be reduced during Carfilzomib or Ibrutinib treatment. In addition, due to an increased risk of venous thromboembolic events associated with Carfilzomib, females should avoid the use of hormonal contraceptives that are associated with a risk of thrombosis during treatment with Carfilzomib. Female patients of childbearing potential who are using oral contraceptives or a hormonal method of contraception that is associated with a risk of thrombosis) or non-hormonal method of highly effective contraception.

The following contraceptive methods are considered highly effective for female patients:

Failure rate of < 1 % per year when used consistently and correctly

- Combined (estrogen and progestogen) hormonal contraception associated with inhibition of ovulation (oral intravaginal [vaginal ring], or transdermal)
- Progestogen-only hormonal contraception associated with inhibition of ovulation (oral, injectable, implantable)

- Intrauterine device (IUD)
- Intrauterine hormonal-releasing system (IUS)
- Bilateral tubal ligation / occlusion
- Vasectomized partner (provided that partner is the sole sexual partner of the female patient of childbearing potential and that the vasectomized partner has received medical assessment of the surgical success)
- Sexual abstinence: Defined as refraining from heterosexual intercourse during the entire period of risk associated with the study treatments. The reliability of sexual abstinence must be evaluated in relation to the duration of the study and the preferred and usual lifestyle of the patient.

If a female patient is suspected of being pregnant, the protocol-required therapies must be stopped immediately and may not be resumed until absence of pregnancy has been medically confirmed.

#### Lactation

It is not known if Carfilzomib or Ibrutinib are transferred into breast milk. If the patient is breastfeeding and wishes to be in this study, they will be required to discontinue nursing during study treatment and for additional 6 months after stopping Carfilzomib or Ibrutinib.

#### Male patients

If the male's sole sexual partner is of non-childbearing potential or has had a bilateral tubal ligation / occlusion, he is nevertheless required to use a condom during treatment and for 6 months after end of treatment. The definition of non-childbearing potential is provided in the chapter before. Male patients with a partner of childbearing potential must agree to not father a child during treatment of Carfilzomib or Ibrutinib and for additional 6 months after the last dose of Carfilzomib or Ibrutinib.

Contraceptive options for male patients include:

- Sexual abstinence (defined as refraining from heterosexual intercourse during the entire period of risk associated with protocol-required therapies). The reliability of sexual abstinence must be evaluated in relation to the duration of the study and the preferred and usual lifestyle of the patient, or
- Use of a condom during treatment of Carfilzomib / Ibrutinib and for additional 6 months after the last dose of Carfilzomib or Ibrutinib. Male patients with a pregnant partner must practice sexual abstinence or wear a condom to prevent exposure of the unborn child to Carfilzomib / Ibrutinib through semen.

#### Unacceptable methods of birth control for male and female patients

Birth control methods that are considered unacceptable in clinical studies include: periodic abstinence (calendar, symptothermal, post-ovulation methods), withdrawal (coitus interruptus), spermicides only and lactational amenorrhea method.

Male and female patients of childbearing potential must receive pregnancy prevention counseling and be advised of the risk to fetus if they become pregnant or father a child or donate sperm during treatment of Carfilzomib and / or lbrutinib and for 6 months after the last dose of Carfilzomib and / or lbrutinib.

Additional medications given during the study may alter the contraceptive requirements. These additional medications may require female patients to use highly effective methods of contraception and for an increased length of time. In addition, male patients may also be required alter the duration and / or methods of contraception. The investigator must discuss these topics with the patients.

### 11.5 Drugs description, storage and handling

#### 11.5.1 Description

In this study, Ibrutinib p.o. and Carfilzomib i.v. are considered as investigational medicinal products (IMP). Ibrutinib will be provided by Janssen, Carfilzomib by Amgen Inc.

Proprietary name:	Imbruvica
Name of substance:	Ibrutinib
Manufacturer:	Janssen
Approved indications:	
 
for the treatment of adult patients with MCL who have received at least 1 prior therapy,
 
CLL/SLL, CLL/SLL with the presence of 17p deletion,
 
WM, MZL who require systemic therapy and have received at least 1 prior anti-CD20-based therapy,
 
and cGvHD after failure of 1 or more lines of systemic therapy.
 
Ibrutinib continues in late-stage development for patients with B-cell malignancies, cGvHD, and solid tumors.
 

Dosage form:	Capsules
Strength:	140 mg
Total daily dose:	420 mg

Proprietary name:	Kyprolis
Name of substance:	Carfilzomib
Manufacturer:	Amgen
Approved indications:	Approved in combination with either Lenalidomide and Dexamethasone or Dexamethasone alone for the treatment of adult patients with multiple myeloma who have received at least one prior therapy
Dosage form:	Infusion

Strength:	60 mg
Total daily dose:	20 mg/m² or 70 mg/m²

## 11.5.2 Storage and handling

#### Ibrutinib

Ibrutinib capsules are provided as a hard gelatin capsule containing 140 mg of Ibrutinib. All formulation excipients are compendial and are commonly used in oral formulations. Refer to the Ibrutinib IB for a list of excipients. The Ibrutinib capsules will be packaged in opaque high-density polyethylene plastic bottles with labels bearing the appropriate label text as required by governing regulatory agencies. All study drugs will be dispensed in child-resistant packaging and will be stored by room temperature. Refer to the site investigational product manual for additional guidance on study drug storage, preparation and handling. Patients receive a handling instruction in their patient diary.

#### Carfilzomib

Carfilzomib is supplied as a sterile, lyophilized, white to off-white powder, ready for reconstitution. It is supplied for single use in 50 mL type 1 glass vials containing 60 mg of Carfilzomib drug product with an elastomeric stopper and flip-off lid. Upon reconstitution with 29 mL of preservative-free sterile water for injection, the reconstituted solution contains 2 mg/mL Carfilzomib, 100 mg/mL sulfobutylether beta-cyclodextrin sodium, and 1.9 mg/mL citrate buffer, at pH 3.0 to 4.0.

Carfilzomib is supplied in labelled cartons containing 4 single use vials per carton. Carfilzomib must be stored between 2°C to 8°C and remain protected from light. Further information will be found in the site investigational product manual.

## 11.5.3 Packaging and labelling

Medication labels will be in the local language and comply with GMP Annex 13 and legal requirements of each country.

## 11.5.4 Supply and ordering

Supplies have to be obtained by sending an order form (located in the ISF) directly to the vendor for Ibrutinib or Carfilzomib. There are no starter supplies. The initial order will be done by the Sponsor after the first patient is in screening at the site. For more information, see the pharmacy manual.

## 11.5.5 Receipt and storage

All drug packages are to be inspected upon receipt at the study site prior to being drawn up. If any particulate matter is detected, the packaging is not to be used. Damaged packaging is to be reported to the sponsor and stored until instructions have been given.

The investigator, the hospital pharmacist or other personnel allowed to store and dispense the IMP will be responsible for ensuring that the IMP used in the clinical study are securely maintained as specified by the sponsor and in accordance with the applicable regulatory requirements. All IMPs must be stored in accordance with labeling and shall be dispensed in accordance with the investigator's prescription. It is the investigator's responsibility to ensure that an accurate record of IMP used and returned is maintained. Any quality issue noticed with the receipt or use of an IMP (deficient IMP in condition, appearance, pertaining documentation, labeling, expiry date, etc.) should be promptly notified to the sponsor, who will initiate a complaint procedure. Under no circumstances will the investigator supply the IMP to a third party, allows the IMP to be used other than as directed by this protocol, or dispose of the IMP in any other manner.

## 11.5.6 Accountability and Compliance

The investigator or pharmacist will inventory and acknowledge receipt of all shipments of the IMP. The investigator or pharmacist will also keep accurate records of the quantities of the study treatments dispensed and used for each patient. The study monitor will periodically check the drug accountability held by the investigator or pharmacist to verify accountability of all used and unused IMP. The sponsor will verify that a final report of drug accountability is prepared and maintained in the investigator study file and trial master file. Administration of the study treatment will be supervised by the investigator or authorized representative.

The dispensing of study drug to the patients and the return of study drug from the patients must be documented on the drug accountability form. Patients must be instructed to return all original containers of Ibrutinib, whether empty or containing study drug. Site staff must not combine contents of the study drug containers. All patients receive a patient diary to document their Ibrutinib intake, any signs and symptoms between site visits and also concomitant medication. Personnel from the study site will review the patient diary during the visit at the site.

## 11.5.7 Destruction of Study Drug

Study drugs such as used and unused study drugs should be destroyed on site. On-site destruction is allowed provided the accountability and disposal records are complete, up-todate, and after release of the sponsor. Used vials can be destroyed after preparation according to local regulations. A potential defect in the quality of the IMP may be initiate a recall procedure by the manufacturer. In this case, the investigator will be responsible for promptly addressing any request made by the manufacturer, in order to recall the IMP and eliminate potential hazards.

## 12. STUDY ASSESSMENTS

A detailed flowchart is provided in Table 1, Table 2 and Table 3 in the synopsis. The schedule of assessment lists all of the assessments and indicates with an "x" when they have to be performed. All data obtained from these assessments must be available in the patient's source documentation. During the course of the study, visits and test procedures should occur on schedule whenever possible; visits that occur  $\pm 4$  days (during treatment, further time window sees flowchart) from the scheduled date will not constitute any protocol deviation.

## 12.1 Screening phase

The signed informed consent form must be obtained before any study specific procedures are performed. The informed consent for the biosampling should be signed before sampling. The patient and the investigator will date and sign the informed consent form. The investigator shall provide a copy of the signed consent to the study patient; the original shall be maintained in the ISF. If a patient signed the informed consent the registration form (available in the ISF) has to be filled and sent to the sponsor via fax or e-mail.

Screening evaluations have to be performed within 45, 30 or 7 days prior to randomization respectively. However, determination of the mutational status of MYD88 and CXCR4 and bone marrow aspirate performed up to 4 months and CT or MRI performed up to 3 months prior to randomization as routine standard of care for the patient's disease can be used. Patients considered eligible by the investigator once all screening procedures are complete and will be randomized to the study on day 0 (see section 12.5).

## 12.2 Active treatment phase

Details of the procedures performed during the treatment phase are described in the flowcharts and in the sections below. All patients will be closely monitored for adverse events, laboratory abnormalities, ECG abnormalities and response. Clinical evaluations and laboratory assessments may be repeated more frequently, if clinically indicated.

Additionally, for the first 10 patients in treatment arm A (Carfilzomib and Ibrutinib) laboratory assessments will be performed on day 8 and 15 of the first 6 cycles. Also, an ECG will be performed on day 15 during the first 6 cycles.

If a patient completes the active treatment phase, an end of treatment visit 30 calendar days after last dose of study treatment has to be performed.

If progression occurs at any time point of the study (i.e. during therapy or during follow up) the assessments described in the flowchart have to be performed (could be combined with another visit of the flow chart, e.g. end of treatment or follow up, depending on what applies). Relapse / progression will be determined by the modified response criteria as published (appendix 21.1). A pathological confirmation by biopsy of the bone marrow or lesion if present should be done if possible.

IgM levels obtained more than 35 days after plasmapheresis can be used in response determination. If disease progression is suspected solely based on the results of a single examination or a single laboratory parameter, this finding should be confirmed by a subsequent evaluation at least within 4 weeks from the first finding. Additional hematologic parameters, radiographic evaluation and bone marrow biopsy should be performed at the discretion of the investigator to confirm progressive disease if indicated.

## 12.3 Follow up phase

As soon as the treatment is stopped because of non-tolerated toxicity, patients will enter followup and will be clinically evaluated every 3 months after the last treatment for 2 years and then every 6 months for 3 additional years or until progression of disease (until end of study).

Patients with progression or starting of new anti-lymphoma therapy will be followed up only for survival data and data with regard to further treatment of WM every 6 months until end of study.

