## Survival Follow-up Phase

All patients who experience a disease progression will be followed for survival every 6 months until the end of the study (7 years after FPI) or death. The same applies to patients who receive a new anti-lymphoma therapy without disease progression.

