The reason for the early termination of the per-protocol treatment must be documented on the respective eCRF page. Patients who stop per-protocol therapy early must be documented and followed-up according to protocol. Early termination should be avoided. In case of an early termination of therapy, reasons / circumstances and if applicable the final disease status of the patient have to be documented. If the patient does not withdraw the consent for further follow-up, he or she should be followed-up as planned.

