#### 14.1.1 Primary Endpoint

The primary endpoint is the rate of CR / VGPR 12 months after randomization.

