## 14.2 Sample size estimation

## RCT - arms A and B:

The sample size calculation is based on the comparison of the primary endpoint (CR / VGPR rate) between the arms A and B using the one-sided chi-square test. According to Treon et al. (NEJM 2015) the CR / VGPR rate in WM patients treated with Ibrutinib is about 16%. We see an increase from 16% to 35% CR / VGPR as a clinically relevant increase, which corresponds to a more than doubling of deep remissions. Deep remissions correlate with PFS and the disease-free interval, thus we assume that the risk-benefit ratio justifies the addition of Carfilzomib when we achieve this improvement. Assuming a CR / VGPR rate of 35% in patients treated with Carfilzomib and Ibrutinib, this scenario requires a number of 94 patients (i.e. 47 patients per group) to reach a power of 80% at a one-sided type one error of 0.10. It is expected that the rate of withdrawal in the study is smaller than 5%. In addition to the drop-out rate of 5%, patients who were randomized but withdrew consent before the start of therapy may be replaced until the end of the recruitment period. According to this, the study will enroll approximately 99 patients in the arms A and B in total.

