## 14.5 Analysis populations

## 14.5.1 Core Analysis Population

The core analysis population consists of all patients randomized in the study evaluated in the group they were randomized to. Patients with missing or unevaluable response assessment12 months after randomization (primary endpoint) will be excluded from analysis of the primary outcome. Patients who progressed or died within 12 months from randomization are not in CR/VGPR at this time point and are thus classified as non-responders (i.e. CR/VGPR="no"). We do not impute missing or unevaluable response assessment because we expect those missing values as missing at random since regular follow-up for lymphoma progression is foreseen also in case of early treatment discontinuation. We will make sure by communication and monitoring that the follow-up schedule will be maintained in case of early treatment discontinuation irrespective of the treatment group. As a sensitivity analysis for the primary outcome, we will perform a conservative imputation of the CR/VGPR rate at 12 months from randomization by defining patients alive without progression and with missing or unevaluable response assessment at this time point as non-responders (i.e. CR/VGPR="no"). The group comparisons of secondary efficacy outcomes represent further sensitivity analyses with different approaches to missing or unevaluable response assessment at 12 months from randomization (e.g. last observation carried forward in best response, counting treatment discontinuation as event in TTF, and censoring at last staging in PFS).

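### The primary analysis treats missing 12-month responses as missing at random because follow-up is said to continue after early discontinuation, but the follow-up rules conflict on most non-toxicity stops and end response assessment when new therapy starts without progression

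*Protocol*

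**What the plan says.** Protocol 14.1.1 sets the endpoint: "The primary endpoint is the rate of CR / VGPR 12 months after randomization". Section 14.5.1 removes patients with a missing or unevaluable 12-month response from the primary analysis. Its ground for missing at random is that "regular follow-up for lymphoma progression is foreseen also in case of early treatment discontinuation", and it undertakes to keep the schedule in both treatment groups. Progression or death before month 12 counts as non-response; new therapy is not mentioned. A sensitivity analysis counts missing responses as non-response.

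The follow-up rules are elsewhere.

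- **Section 12.3:** "As soon as the treatment is stopped because of non-tolerated toxicity, patients will enter followup and will be clinically evaluated every 3 months". The synopsis (Follow-up Phase) and the duration table in 9.1 also tie this phase to a stop for toxicity.
- **Section 12.3, next paragraph:** "Patients with progression or starting of new anti-lymphoma therapy will be followed up only for survival data", plus data on further WM treatment. The synopsis (Survival Follow-up Phase) gives the rule for progression and adds: "The same applies to patients who receive a new anti-lymphoma therapy without disease progression". Section 9.1 and the text above Table 3 agree.
- **Section 12.7.1:** lists further reasons to stop, among them patient decision, investigator decision, intercurrent illness and non-compliance, and then says: "Patients who stop per-protocol therapy early must be documented and followed-up according to protocol". Unless consent to follow-up is withdrawn, these patients are to be followed as planned.
- **Table 3:** the follow-up column is placed after the end-of-treatment visit, with no toxicity condition.

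**The concern.** Leaving patients out of the primary comparison is defensible only if their absence is unrelated to their response. Section 14.5.1 rests that assumption on continued follow-up, so the follow-up rules have to deliver it. There are two weak points.

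1. **Stops for reasons other than toxicity or progression.** Section 12.7.1 sends these patients to the protocol's follow-up, but the section describing that follow-up has no entry for them. A site that works from 12.3 could reasonably schedule nothing.
2. **New therapy without progression.** Here the texts agree with one another and contradict 14.5.1: response assessment ends. If the switch comes before month 12, the response is missing by design and the patient leaves the primary analysis. A patient given another drug for the disease is more likely than average to be short of CR/VGPR. Removing such patients raises the observed rate in the arm that loses more of them.

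PFS in 14.1.2 is touched too. New therapy is not a PFS event, so a switcher who is alive with no recorded progression is censored at the latest tumor assessment, and survival-only follow-up no longer looks for the progression.

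**Working it through.** **Step 1: reproduce the design.** Inputs from 14.2: 16% in arm B, 35% in arm A, one-sided alpha 0.10, power 80%; 1:1 allocation from 12.5. The mean rate is 0.255.

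n per arm = [z(0.90)·√(2·0.255·0.745) + z(0.80)·√(0.35·0.65 + 0.16·0.84)]² / (0.35 − 0.16)²
= [1.2816·0.6164 + 0.8416·0.6016]² / 0.0361 = 46.5, rounded up to 47.

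That is 94 in total, with power 0.803 at 47 per arm. Allowing 5% dropout, 94/0.95 = 98.9, so 99. The stated figures reproduce and none of them is wrong.

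**Step 2: trace each kind of early stop.**

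| Stop before month 12 | 12.3, 9.1, synopsis | 12.7.1, Table 3 | 14.5.1 |
|---|---|---|---|
| Toxicity | 3-monthly follow-up | follow-up | response observed |
| Progression | survival only | progression assessments, then survival only | non-responder |
| Patient or investigator decision, intercurrent illness, non-compliance | no route named | follow-up as planned | presumes follow-up |
| New therapy without progression | survival only | Table 3: survival only | not classified; excluded if response missing |

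Survival-only follow-up after progression does no harm to the primary endpoint, because those patients are non-responders by rule. The third row is a conflict between sections. In the fourth row no passage restores the 12-month response.

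**Step 3: size.** The protocol gives no rate for non-toxicity stops or for early switches, so all exclusion rates below are assumed.

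*Loss of power alone.* With 99 enrolled, 16% versus 35% among those analysed and equal exclusion in both arms, power is 0.803 at 5% excluded, 0.787 at 10%, 0.769 at 15% and 0.750 at 20%.

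*Selective loss.* Let the true rate among all randomized patients be 16% in both arms and let every excluded patient be a non-responder. The rate among those analysed is then 0.16/(1 − m), where m is the excluded fraction. The test statistic is Z = (xA/nA − xB/nB) / √[p̄(1 − p̄)(1/nA + 1/nB)], with rejection at Z ≥ 1.2816. Summing the exact binomial probabilities of rejection gives:

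| Excluded A / B | Analysed A, B | Rates A, B | One-sided type I error |
|---|---|---|---|
| 0% / 0% | 50, 50 | 0.160, 0.160 | 0.100 |
| 0% / 0% | 50, 49 | 0.160, 0.160 | 0.108 |
| 5% / 0% | 47, 50 | 0.168, 0.160 | 0.116 |
| 10% / 0% | 45, 49 | 0.178, 0.160 | 0.155 |
| 10% / 5% | 45, 47 | 0.178, 0.168 | 0.123 |
| 15% / 5% | 42, 47 | 0.188, 0.168 | 0.163 |
| 10% / 10% | 45, 45 | 0.178, 0.178 | 0.105 |

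The two reference rows show that discreteness alone moves the result by just under 0.01. The 10% / 0% row means five patients: 5/99 = 5.1%, about the whole dropout allowance of 14.2, all falling in arm A. If the loss falls on arm B instead (50 and 45 analysed, rates 0.160 and 0.178), the same sum gives about 0.07, so the direction depends on which arm loses more.

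**The case against.** The strongest reply is that 12.7.1 already requires follow-up of everyone who stops early. Table 3 sets no toxicity condition, 9.1 opens with a general sentence that patients are followed after treatment, and 14.5.1 promises to secure the schedule by communication and monitoring. This stands as far as it goes. A reader might infer that data after discontinuation are simply not collected, and the protocol does not support that. Patients who stop for toxicity have immunoglobulins at each follow-up visit and, where applicable, 6-monthly CT. For the other non-progression stops the fault is conflicting text. The reply does not help switchers.

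The non-responder sensitivity analysis also limits the damage, but it is not the analysis on which the trial's conclusion is drawn. TTF counts new therapy as an event, but PFS does not.

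Three further inferences are tempting and should not be drawn.

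- **A stated bias in PFS.** Any figure needs an assumed switch rate and an assumed hazard after the switch. If switching is unrelated to prognosis, the gap between censoring and continued follow-up is a difference between two estimands, and it reverses if the new therapy works well.
- **No usable visit near month 12 for early stoppers.** The protocol sets no narrow window around day 365. Patients on treatment are themselves assessed at cycle 13 day 1, nominally day 12 × 28 + 1 = 337 counted from cycle 1 day 1.
- **A gap peculiar to arm A** for patients who finish carfilzomib alone. This arises only after cycle 24, past the primary endpoint. Since ibrutinib must have been stopped for toxicity, such a patient can be read as already on the toxicity route.

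**Conclusion.** The point holds in two parts. First, 12.3, 9.1 and the synopsis conflict with 12.7.1, Table 3 and 14.5.1 on follow-up after a stop for reasons other than toxicity or progression. Second, patients who start new therapy without progression before month 12 have no scheduled response and no classification, so the primary analysis drops them on a premise that the protocol's own follow-up rules contradict.

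The size cannot be fixed from the document. Under the assumptions shown, the harm is small when the arms lose equally (type I error about 0.105, power down by about 5 points at most with 20% excluded). It is material when one arm loses more: about 0.155 with 10% against 0%, provided every excluded patient is a non-responder. That proviso is the unfavourable extreme. The sample size is unaffected. This should be corrected in the protocol, because an analysis plan cannot recover assessments that the protocol tells sites to stop.

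**What to change.** 1. **Follow-up route.** Reword 12.3, 9.1 and the synopsis to agree with 12.7.1, Table 3 and 14.5.1: every patient who ends study treatment without progression, for whatever reason and without withdrawing consent to follow-up, enters the Table 3 follow-up phase.
2. **Primary endpoint.** In 14.5.1, count new anti-lymphoma therapy started before the 12-month assessment without progression as CR/VGPR = no in the primary analysis. This removes the exclusion without extra visits and keeps a response on another drug from being credited to the randomized arm.
3. **PFS.** Make sure that the start date of new therapy is recorded (Table 3 already has a row for it). After a switch without progression, keep the Table 3 progression assessments until progression or end of study, and use survival-only follow-up after that.

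The cost is amendment wording and some extra eCRF documentation for a minority of patients. The text above Table 3 describes its assessments as routine WM follow-up, so no new procedure is needed.
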